8.2. Schedule of Visits and Assessments

The schedule of assessments is shown in Table 3.

For a missed visit, the site should attempt to contact the subject to reschedule.

Premature discontinuation procedures are provided in Section 7.3.

Table 3: **Schedule of Assessments**

| | | Treatmo | ent Period ^a | | Follow-up Period ^a |
|---|--|---|------------------------------------|---------------------------|---|
| Visits 1-25 ^b | Transition from Previous Study ^c | Monthly Visits ^d | Quarterly Visits | EOT/ ET | Safety Follow-up Visit ^e |
| | 1 | 2, 3, 5, 6, 8, 9, 11, 12, 14, 15, 17, 18, 20, 21, 23, 24 | 4, 7, 10, 13, 16, 19, 22, 25 | | No later |
| Visits 26-50 ^b | _ | 26, 27, 29, 30, 32, 33, 35, 36, 38, 39, 41, 42, 44, 45, 47, 48 | 28, 31, 34, 37, 40, 43, 46 | No later than Visit 49 | than Visit 50 |
| Qualification/ Safety Assessments | | | | | |
| Informed Consent | X | | | | |
| Eligibility Review | X | | | | |
| Urine Pregnancy Testing (all women) | X | X | X | X | X |
| Urine Drug Screen | X^{f} | | X | | |
| Physical Examination and ECG | | | X | X | |
| Vital Signs | | | X | X | |
| Biochemistry, Hematology, and Urinalysis Samples | | | X | X | |
| Weight and Waist Circumference | | X | X | X | X |
| Adverse Event Monitoring | | X | X | X | X |
| Concomitant Medication Review | | X | X | X | X |
| C-SSRS ^g | | X | X | X | X |
| Psychiatric/ Quality of Life Assessm | nents | | | | |
| CGI-S | | X | X | X | X |
| IWQOL-Lite | | | X | X | |
| Other/ General Procedures | | | | | |
| Study Drug Dispensation | X | X | X | | |
| Study Drug Return Review | | X | X | X | |

Abbreviations: CGI-S=Clinical Global Impressions-Severity; C-SSRS=Columbia-Suicide Severity Scale; ECG=electrocardiogram; EOT=end of treatment; ET=early termination; IWQOL-Lite=Impact of Weight on Quality of Life-Lite

A visit window of ±4 days is allowed throughout the treatment period and the Follow-up period.

- ^b Subjects may be treated with study drug for 24 to 48 months, or until regulatory action; duration will vary by subject.
- ^c Visit 1 must occur within 7 days of the EOT visit of the antecedent studies (ALK3831-A304, ALK3831-A306, or ALK3831-A307) and may occur on the same day. Subsequent visits are to be conducted every month (every 28 days [±4 days]).

 d Except for every 3rd visit from Visit 1 (Quarterly Visits).
- To be performed one month (28 days [±4 days]) after the EOT/ET visit.
- The urine drug screen will be performed at Visit 1; however if Visit 1 is the same as EOT visit of the antecedent study and a urine drug screen was already performed during that visit, it doesn't need to be repeated.
- ^g 'Since Last Visit' version to be used at all indicated visits.

8.3. Study Procedures Descriptions

Details of the study procedures are described below. The overall schedule of assessments is provided in Table 3.

8.3.1. Informed Consent

The nature of the study and its risks and benefits will be explained to the subject by the Principal Investigator (PI) or designated study personnel as outlined in Section 17.3.

Prior to the administration of any study-specific procedures, authorized study personnel will obtain written informed consent/assent as per local requirements from each potential subject as specified in Table 3.

8.3.2. Eligibility Review

An eligibility review will be conducted by the Investigator at the visits specified in Table 3 using the subject inclusion criteria in Section 7.1 and exclusion criteria in Section 7.2.

8.3.3. Demographics and Medical / Psychiatric History

Subject's demographic data and medical / psychiatric history (including primary psychiatric diagnosis) will be carried over from the antecedent studies (ALK3831-A304, ALK3831-A306, or ALK3831-A307).

8.3.4. Concomitant Medication Review

At the timepoints specified in Table 3, subjects will be asked about the medications they have taken since their last visit, including prescription and nonprescription medications, vitamins, and supplements.

The investigator will record the following data on all medications used by the subject: name, dose, regimen, route of administration, start and stop dates, and the indication for use.

8.3.5. Vital Signs

Vital signs (ie, blood pressure, pulse, respiratory rate, and oral body temperature) will be assessed at the timepoints specified in Table 3. An effort will be made to consistently use the same arm (preferably the subject's dominant arm) to measure blood pressure and heart rate throughout the study. The blood pressure cuff will be calibrated per study site standard operating procedures. Automated measurement is preferred, but if performed manually, heart rate will be measured in the brachial artery for at least 30 seconds.

Blood pressure, heart, and respiratory rate will be measured after the subject has been in the supine position for at least 5 minutes. Vital signs may be collected at any time during a scheduled visit, unless otherwise noted.

8.3.6. Physical Examination

A brief physical examination and an ECG (local) will be performed at the timepoints specified in Table 3.

8.3.7. Weight and Waist Circumference

Weight and waist circumference will be measured at all the timepoints specified in Table 3.

For weight measurements, subjects should be asked to void immediately prior to measurement and should be dressed in a hospital gown with consistent under-attire for each measurement. Subjects should remove all personal items (including shoes, watches, and jewelry) and they should be weighed on the same scale for each measurement under the same conditions.

Both weight and waist circumference will be measured three consecutive times at each assessment and all measurements will be recorded in the eCRF.

8.3.8. Structured Interviews and Questionnaires

Brief descriptions of each of the interviews and questionnaires to be distributed are available below. All interviews and questionnaires will be administered by trained and qualified study personnel.

For assessments performed at multiple visits, every effort should be made to pair the same clinician / rater with the same subject across visits.

Table 3 provides information on the timepoints at which each assessment should be administered.

8.3.8.1. Safety Assessments

8.3.8.1.1. Columbia-Suicide Severity Rating Scale

The PI or designee will administer C-SSRS according to the timepoints in Table 3. The "Since Last Visit" version of the C-SSRS will be used at all indicated visits. The C-SSRS should be administered by a qualified clinician trained in assessing and managing suicidal ideation and behavior (Posner et al, 2011).

8.3.8.2. Psychiatric/Quality of Life Assessments

8.3.8.2.1. Clinical Global Impressions-Severity

The PI or designee will complete the CGI-S scale at the timepoints specified in Table 3. The CGI-S measures mental illness severity. Clinicians are asked to rate subjects based on their prior experience working with individuals in a similar patient population (Guy 1976).

8.3.8.2.2. Impact of Weight on Quality of Life-Lite

Subjects will complete the IWQOL-Lite questionnaire (Kolotkin et al, 2001) at the timepoints specified in Table 3.

8.3.9. Laboratory Assessments

8.3.9.1. Drug Testing

A urine drug test for opioids and drugs of abuse, including amphetamine/methamphetamine, phencyclidine, and cocaine, will be performed at the timepoints specified in Table 3. Results must be negative for the subject to be eligible for the study. The urine drug screen will be

performed at Visit 1; however if Visit 1 is the same as the end of treatment visit of the antecedent study and a urine drug screen was already performed during that visit, it doesn't need to be repeated. The urine drug screen may be repeated at any point during the study based on the investigator's discretion.

8.3.9.2. Hematology, Biochemistry, and Urinalysis

Blood and urine samples for laboratory assessments will be collected at the timepoints specified in Table 3. Specific hematology, biochemistry, and urinalysis assessments are listed in Table 4. Subjects will be instructed not to eat or drink anything (except water) for 8 hours before each visit where blood samples for biochemistry and hematology assessments will be collected. Samples will be collected in accordance with the site's usual procedures and analyzed by a central laboratory. Laboratory assessments may be repeated at the Investigator's discretion.

Table 4: Clinical Laboratory Assessments

| Hematology | Biochemistry | Urinalysis |
|-----------------------------------|-----------------------------|-------------------------------|
| Hematocrit | General Chemistry | Bilirubin |
| Hemoglobin | Albumin | Color and appearance |
| Platelets | Bicarbonate | Glucose |
| Red blood cell count | Calcium | Ketones |
| Total and differential (absolute) | Chloride | Leukocytes |
| white blood cell count | Creatine phosphokinase | Nitrite |
| | Glucose | Occult blood |
| | Lactic dehydrogenase | рН |
| | Potassium | Protein |
| | Sodium | Specific gravity |
| | Total protein | Urobilinogen |
| | Uric acid | Cotinine |
| | Endocrine Function Test | Microscopic examination of |
| | HbA1c | sediment, only if urinalysis |
| | Prolactin | dipstick results are abnormal |
| | Insulin | |
| | Liver Function Tests | |
| | Alanine aminotransferase | |
| | Alkaline phosphatase | |
| | Aspartate aminotransferase | |
| | Gamma-glutamyl transferase | |
| | Total bilirubin | |
| | Renal Function Tests | |
| | Blood urea nitrogen | |
| | Creatinine | |
| | Lipid Panel | |
| | High-density lipoprotein | |
| | Low-density lipoprotein | |
| | Total cholesterol | |
| | Triglycerides | |

8.3.9.3. Urine Pregnancy Testing

A urine pregnancy test will be administered to all women at the timepoints specified in Table 3. At Visit 1, results must be negative for the subject to be eligible for the study. As highlighted in Section 7.3, a positive pregnancy test result at any time will necessitate the subject's immediate withdrawal from the study. Additional follow-up may be necessary as indicated in Section 8.4.1.

8.3.10. Drug Dispensation and Reconciliation

Section 9 provides information related to drug dispensing procedures. Study drug will be dispensed/administered at the timepoints specified in Table 3. The study drug use and storage information will be explained to/reviewed with the subject.

8.3.11. Emergency Treatment Card

An emergency treatment card will be distributed to each subject at Visit 1 and collected at the EOT/ET Visit. The card will indicate that the subject is receiving an opioid antagonist and olanzapine and will include the PI's contact information, a suggested pain management plan and information regarding opiate blockade. Subjects will be instructed to keep the card with them at all times. Study personnel will confirm that subjects have the card in their possession at each study visit.

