7.3. Subject Withdrawal

A subject may be discontinued from the study at any time if the subject, Investigator, or Sponsor determines that it is not in the best interest of the subject to continue participation. If a subject has an absolute neutrophil count (ANC) $< 1.0 \times 10^3$ per μ L or Hemoglobin A1c (HbA1c) $\ge 6.5\%$ at any time, the PI (or designee) should discontinue the subject from participation immediately. Reasons for discontinuation include:

- Adverse Event
- Lack of Efficacy
- Lost to Follow-up
- Withdrawal by Subject
- Protocol Deviation (including non-compliance with study drug or study procedures)
- Pregnancy
- Study Terminated by Sponsor
- Other

If a subject withdraws from the study for any reason, any ongoing AEs will be followed until resolution, until deemed stable by the Investigator, or until the subject is deemed by the Investigator to be lost to follow-up. If, in the opinion of the Investigator, it is necessary to monitor a subject beyond the safety follow-up visit, the follow-up period may be extended as necessary. In such instances, the Sponsor and Investigator will agree to an acceptable follow-up schedule.

In the event that a subject chooses to withdraw from the study, the Investigator should make a reasonable effort to ascertain the reason(s) for withdrawal, while fully respecting the subject's rights. Subjects who terminate the treatment early (prior to Visit 25) will complete an early termination (ET) visit and the 4-week Safety Follow-up period. The ET visit should be scheduled as close as possible to the subject's last dose and will mimic the assessments scheduled to be conducted at the EOT Visit. If the subject fails or refuses to return to the study center, an attempt must be made to contact the subject by telephone in order to assess as many safety and efficacy parameters as possible. All data collected over the telephone must be documented and kept in the subject's record.

The Investigator must maintain a record of all subjects who fail to complete the study. The reason for study discontinuation will be documented and made on the appropriate electronic case report form (eCRF). If a subject is lost to follow-up, a reasonable attempt to contact the subject must be made and documented.

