8.4.4. Pain Management

Because ALKS 3831 contains samidorphan, a μ-opioid antagonist, patients may experience reduced or ineffective analysesia when taking an opioid analysesic agent concurrently with ALKS 3831, including several days after last dosing of ALKS 3831.

In the event of an emergency, pain management of the subject should include the following:

- Regional analgesia or use of non-opioid analgesics
- If opiate anesthesia or analgesia is required, the subject should be continuously monitored, in an anesthesia care setting, by persons not involved in the conduct of the surgical or diagnostic procedure. The opioid therapy must be provided by individuals specifically trained in the use of anesthetic drugs and the management of the respiratory effects of potent opioids, specifically the establishment and the maintenance of a patent airway and assisted ventilation
- Close monitoring by appropriately trained personnel in a setting equipped and staffed for cardiopulmonary resuscitation

For subjects requiring emergency opioid analgesics prior to dosing, the study drug should not be administered. If opioid analgesics are required after the study drug has been dosed, it may take several days for opiate sensitivity to be restored, since samidorphan functions as a μ -opioid antagonist and could interfere with opioid-mediated pain management.

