10.2. Packaging and Labeling

ALKS 3831 will be supplied in blister packs. Blister cards will be in biweekly configurations. Biweekly blister cards will contain 16 tablets, enough for 2 weeks of dosing plus sufficient overage for 2 additional once daily doses.

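### The emergency card is taken back at EOT/ET, although the protocol says opioid blockade may last several days after the last dose

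*Protocol*

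**What the plan says.** Protocol section 8.3.11 sets out how the card is handled: "An emergency treatment card will be distributed to each subject at Visit 1 and collected at the EOT/ET Visit". On content, "The card will indicate that the subject is receiving an opioid antagonist and olanzapine". The card also gives the investigator's contact details, a suggested pain management plan and information on opiate blockade. Subjects must carry it at all times, and staff check for it at every study visit.

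Section 8.4.4 says twice that the blockade outlasts dosing. Opioid analgesia may be reduced or ineffective while a subject takes ALKS 3831, "including several days after last dosing of ALKS 3831". If opioids are needed after a dose has been taken, "it may take several days for opiate sensitivity to be restored". Neither statement gives a number of days.

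On timing, section 7.3 says: "The ET visit should be scheduled as close as possible to the subject's last dose". For subjects who do not attend: "If the subject fails or refuses to return to the study center, an attempt must be made to contact the subject by telephone". Table 3 shows no drug dispensed at EOT/ET and places the Safety Follow-up Visit 28 ±4 days later. No section lets the subject keep the card, or gives a replacement, after EOT/ET.

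**The concern.** Section 8.3.11 ends the card's use at a visit. Section 8.4.4 ties the hazard to the time since the last dose. When the visit falls close to the last dose, the card goes back to the site while the hazard it warns about may still be present. A site that follows section 7.3 well, and sees the subject promptly, creates the larger gap.

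The protocol describes no other carried alert. Section 17.3 gives the subject a copy of the signed consent form, but the subject is not asked to carry it, and its content was not available for this review.

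What is at stake is the care of a subject who needs emergency analgesia in the first days after EOT/ET, above all one who cannot speak. If opioids are required, section 8.4.4 asks for continuous monitoring in an anesthesia care setting, staff trained in the respiratory effects of potent opioids, and resuscitation capability. The card is how that plan reaches an outside team. Without it, the team has no written prompt to apply these measures.

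**Working it through.** The plan gives no figure on this point, so there is nothing to reproduce. The check sets the timing rules side by side and then bounds the gap.

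**1. Can EOT/ET fall inside the blockade period?**

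- *ET:* yes, by instruction. Section 7.3 asks for the visit as near as possible to the last dose.
- *Scheduled EOT:* the documents do not say that dosing continues up to the visit, so this is an assumption. The supply allows it. Section 10.2 says: "Biweekly blister cards will contain 16 tablets, enough for 2 weeks of dosing plus sufficient overage for 2 additional once daily doses". Visits are every 28 days with a window of ±4 days (Table 3 footnotes). One card of 16 tablets cannot cover 28 days, so at least two are needed per interval; that number is inferred. Then 2 × 16 = 32 tablets, and 28 + 4 = 32 days. Once-daily dosing can therefore run up to an EOT visit at the late end of its window. Bedtime dosing is preferred (section 9.1) and nothing is dispensed at EOT, so a last dose on the evening before the visit (d = 1) is a reasonable near case.

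**2. Size of the gap for one subject**

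Let B = days of blockade after the last dose, and d = days from the last dose to EOT/ET.

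Uncovered days = max(0, B − d)

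The documents give neither value. Taking B = 2 to 7 days as an illustrative reading of several days:

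| d (days) | B = 2 | B = 7 |
|---|---|---|
| 1 | 2 − 1 = 1 | 7 − 1 = 6 |
| 3 | max(0, 2 − 3) = 0 | 7 − 3 = 4 |
| 7 | max(0, 2 − 7) = 0 | 7 − 7 = 0 |

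A second set of assumptions, B = 3 to 7 and d = 0 to 1, gives 3 − 1 = 2 up to 7 − 0 = 7 days. Both sets show a gap of days when the visit is prompt. The gap vanishes only when the visit comes after the blockade has ended.

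**3. Does anything later in the schedule close the gap?**

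No. The next scheduled visit is 28 − 4 = 24 to 28 + 4 = 32 days after EOT/ET, well beyond any B considered here. The rule that staff check for the card at every study visit also cannot be met at the Safety Follow-up Visit, because the card has already been collected.

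**4. Who is not affected?**

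Subjects who stopped dosing several days before the visit have little or no gap. Those who never return and are only telephoned do not hand the card in. The number in each group cannot be derived from the documents, nor can the rate at which emergency opioids are needed.

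**The case against.** The strongest reply accepts the mismatch and disputes its weight.

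- *The size is assumed.* This stands. The documents say only several days, the range above includes zero, and it should be read as an illustration.
- *The event is rare.* The gap occurs once per subject, lasts days, and follows up to 48 months of treatment. Harm needs an emergency requiring opioids in that window and a subject who cannot report recent treatment, after months of being told to carry the card. This lowers the likelihood of harm. It does not help the incapacitated subject, for whom a carried card matters most.
- *Collection may be deliberate.* A card saying that the subject is on an opioid antagonist becomes untrue after treatment ends, and a team that trusts it could withhold opioids that would work. The protocol does not give this reason, but the risk is real. It argues for an expiry date on the card, not for removing the card while the blockade may still be active.
- *The card text is not reproduced.* Also true: its blockade information may already cover the days after the last dose. Even so, that text is of no use once the card has been handed in. The wording change proposed below addresses only what section 8.3.11 says the card will state.
- *The fix is incomplete.* Subjects reached only by telephone would keep an undated card. They already do under the current text, so they are no worse off.
- *Amendment has a cost.* Section 17.1 requires the ethics committee to re-approve amendments, and section 17.3 allows that consent forms may need revision. This stands and is counted below.

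**Conclusion.** The concern holds. Followed as written, sections 7.3 and 8.3.11 remove the only carried alert that the protocol describes during a period that section 8.4.4 identifies as one of reduced or absent opioid effect. For a subject seen one day after the last dose, the uncovered time is 1 to 6 days if blockade lasts 2 to 7 days; it shrinks to nothing as the visit moves later.

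The conflict rests on the protocol's text alone. The day counts rest on assumed values of B and d, and for the scheduled EOT on the further assumption that dosing continues to the visit. The number of subjects exposed and the expected harm are unknown. This is a subject-safety point with no effect on any endpoint, population or analysis. It should be changed because the possible harm is serious and the remedy is small. Confidence is medium.

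**What to change.** Amend section 8.3.11 as follows:

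1. At EOT/ET the site writes two dates on the card: the date of the last dose, and a blockade expiry date equal to the last dose plus a number of days stated by the sponsor.
2. The subject carries the card until the expiry date and returns it at the Safety Follow-up Visit.
3. The card states that the subject is receiving, or has recently received, an opioid antagonist.

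Return at the Safety Follow-up Visit also makes the card check at every study visit workable.

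The cost is one or two protocol sentences, two date fields on the card, a number of days that only the sponsor can supply, and a site instruction. Ethics committee re-approval goes with any amendment, and consent forms may need an update. No visit or procedure is added. Some cards will not come back. A retained card without its dates could lead a team to withhold opioids after sensitivity has returned, so the dates are an essential part of the change.

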8.3.12. Adverse Event Monitoring

All AEs will be monitored continuously from the time a subject signs the informed consent document until the completion of the final study visit (see Table 3). All AEs ongoing at the end of trial or concomitant medications continuing from the antecedent study will be carried over and followed until resolution. All AEs and serious adverse events (SAEs) are defined in Section 13.2 and Section 13.3, respectively. Section 13.5 provides guidance on the monitoring and recording requirements for AEs. Section 13.6 provides guidance on the reporting requirements for SAEs.

8.4. Study Requirements and Restrictions

8.4.1. Contraception and Pregnancy

All male and female subjects must agree to use an acceptable method of contraception for the duration of the study. All female subjects must agree to use an acceptable method for 30 days after the last dose of study drug, unless they are surgically sterile or postmenopausal (see below). The following are considered acceptable methods of contraception:

- 1. Intrauterine device
- 2. Oral contraceptive pills and other hormonal methods (eg, a vaginal ring, contraceptive patch, contraceptive implant)
- 3. Double-barrier protection (eg, a condom with spermicide or a diaphragm with spermicide)
- 4. Abstinence (see below)

Subjects who are abstinent are eligible, provided they agree to use an acceptable contraceptive method should they become sexually active. Abstinence is defined as "true abstinence" in which subjects must refrain from heterosexual intercourse for the full duration of the study and must be in line with the preferred and usual lifestyle of the subject. Periodic abstinence (eg, calendar, ovulation, symptothermal, postovulation methods), declaration of abstinence for the duration of exposure to the study drug, and withdrawal are not acceptable methods of contraception.

Subjects who are surgically sterile are exempt from the requirement to use contraception. Women who have undergone a hysterectomy, bilateral tubal ligation, or bilateral

salpingo-oophorectomy are considered surgically sterile. Men who have undergone a vasectomy are considered surgically sterile. Partner vasectomy is not considered an approved acceptable method of contraception for a female subject.

Women who are postmenopausal are also exempt from the requirement to use contraception. For the purpose of this study, postmenopausal is defined as the permanent cessation of menstruation for at least 12 months prior to Screening in women who are 45 years of age or older.

If a subject becomes pregnant while participating in the study, she will be discontinued from study drug immediately. The ET and safety follow-up visits will be scheduled and the pregnancy will be reported to Alkermes. Additional follow-up may be required. Pregnancies in female partners of male subjects should also be reported and will be followed in the same manner. If a male subject has a partner who becomes pregnant, the partner may need to provide written informed consent to obtain pregnancy follow-up information, as per local requirements.

A Pregnancy Report Form must be submitted to Alkermes via (per Section 13.6) immediately, within 24 hours of awareness of the pregnancy, irrespective of whether an AE has occurred. The pregnancy will be followed until completion or termination. If the outcome of the pregnancy meets the criteria for classification as an SAE, it should be reported following the SAE procedure (see Section 13.6).

